STUDY PROTOCOL

Genetic Determinants of the Coronary Microvascular Obstruction in Percutaneous Coronary Interventions

Study Title:	Genetic Determinants of the Coronary Microvascular Obstruction in Percutaneous Coronary Interventions
Protocol Number:	CMVO-SNP-2022
Study Number:	NCT05355532
Document date and version:	Version number 1 from April 24, 2022
Sponsor:	Privolzhsky Research Medical University
Principal Investigator:	
Principal Investigator: [name] [name]
 
Research Center: State Budgetary Healthcare Institution of Nizhny Novgorod Region "City Clinical Hospital No. 13 of Avtozavodsky District of Nizhny Novgorod"
 
Research Center Address: [name]
 
Research Center [contact]

Study Rationale

For decades, ischemic heart disease (IHD) has been the leading cause of mortality in developed countries. Currently, percutaneous coronary intervention (PCI) is the primary method for restoring blood flow in the coronary artery (CA) in IHD, significantly reducing mortality in myocardial infarction (MI) and improving quality of life in stable angina. However, in 5–10% of cases, PCI leads to coronary microvascular obstruction (CMVO, or "no-reflow")—a phenomenon characterized by the absence of adequate myocardial perfusion despite successful restoration of epicardial coronary artery patency [1]. CMVO substantially worsens prognosis and can be a direct cause of death [1].

The pathogenesis of CMVO is complex and involves multiple concurrent mechanisms with varying degrees of contribution [1]. The most significant clinically established predictors of CMVO include: age, time from symptom onset to reperfusion, severity of acute heart failure (Killip classification), ineffective prehospital thrombolytic therapy, collateral blood flow (Rentrop classification) [6], coronary artery thrombus burden (TIMI thrombus grade) [7], baseline coronary flow (TIMI flow grade) [8], implantation of ≥ 3 stents during PCI, direct stenting of the target artery, blood neutrophil and glucose levels [2–5].

The pathophysiological heterogeneity of CMVO makes its prediction challenging. Even the best available models [2–5] demonstrate limited positive predictive value (60–70%). This limitation may stem from the omission of genetic factors influencing endothelial function, microcirculation, hemostasis, and inflammation in current models.

Identifying genetic determinants of CMVO holds significant scientific novelty and could form the basis for a novel diagnostic system to predict this complication. Such a system would be clinically valuable, reducing PCI-related risks and improving patient outcomes.

Study Objective: to identify genetic determinants of coronary microvascular obstruction development during percutaneous coronary interventions.

Study Design

A matched case-control study will be conducted to examine the role of specific single nucleotide polymorphisms (SNPs) as predictors of coronary microvascular obstruction (CMVO) development. The study will enroll 80 patients meeting the inclusion/exclusion criteria who have provided written informed consent. Patients will be allocated into two groups in a 1:1 ratio:

- Group 1 (CMVO+): 40 patients with myocardial infarction (MI) who developed CMVO following PCI
- Group 2 (CMVO-, control group): 40 patients with MI who did not develop CMVO following PCI

Group allocation will be performed by the principal investigator. The groups will be matched by sex and age using the "matched pairs" method [9]. For each patient in the CMVO+ group, a corresponding patient of the same sex and similar age (± 5 years) will be selected from the pool of MI patients who underwent PCI without CMVO development.

The required sample size (80 patients) was determined based on the following parameters: alpha error level – 5 %, study power – 80 %, group ratio – 1:1, minimum detectable odds ratio – 4.0, expected prevalence of the studied SNPs in the population: 12–69 % (average 50%) [10]. Among the 40 planned matched pairs, 20 pairs must be discordant (i.e., the paired patients must differ in the presence or absence of the predictor).

The study will be conducted in several stages:

1. Patient Screening

- The principal investigator will assess inclusion/exclusion criteria.
- Determine eligibility for study group allocation.
- Performed in the catheterization laboratory immediately after PCI completion.

2. Informed Consent Process

- Eligible patients will provide written informed consent for genetic testing.

- Patients will be assigned to respective study groups.
- Conducted in the catheterization laboratory.

3. Biological Sample Collection

- Blood sampling for genetic analysis.
- Performed in the catheterization laboratory.

4. Sample Processing and Transportation

- Blood sample processing.
- Transportation to the Central Research Laboratory of the Institute of Fundamental Medicine at Privolzhsky Research Medical University (Russian Ministry of Health).

5. Clinical Data Collection

- The investigator will complete patient registry forms.
- Includes hospitalization course and outcomes.

6. Genetic Analysis

- Performed at the Central Research Laboratory of the Institute of Fundamental Medicine at Privolzhsky Research Medical University.

7. Data Management

- Collected information will be entered into a unified electronic database.

8. Statistical Analysis

- Comprehensive processing of all obtained data.

Ethical Information About the Study

The study is conducted in accordance with Good Clinical Practice (GCP) standards and the principles of the Helsinki Declaration. The study protocol has been approved by the local ethics committee. Patient information is processed anonymously. Upon inclusion in the study, each patient is assigned a serial number. The following data are recorded in the registry of enrolled patients: serial number, last name, first name, patronymic, sex, date of birth, study group, date of inclusion in the study, medical record number, contact phone number, home address, pair number. This registry is stored at the research center. The serial number is indicated on: the

inclusion/exclusion criteria form; the patient's voluntary informed consent for study participation; blood collection tubes with patient samples; the patient registry form with hospitalization details and outcomes; the unified electronic database of study participants. All work with blood samples outside the research center and statistical processing of obtained data is performed in anonymized form.

Inclusion Criteria:

1. Signed voluntary informed consent for study participation by the patient;
2. Male or female aged 18 years or older;
3. ST-segment elevation myocardial infarction (STEMI) type I according to the Fourth Universal Definition of Myocardial Infarction criteria [11] and current clinical guidelines for this condition [12];
4. Enrollment in the study immediately after PCI with possibility of blood sampling in the catheterization laboratory after signing informed consent;
5. For "CMVO+" group: Development of CMVO as a result of PCI (CMVO is assessed according to criteria specified in the European Society of Cardiology clinical guidelines) [12];
6. For "CMVO-" group: Absence of CMVO as a result of PCI (CMVO is assessed according to criteria specified in the European Society of Cardiology clinical guidelines) [12] and matching with the paired patient from "CMVO+" group by sex and age (± 5 years).

Exclusion Criteria:

1. Presentation with subacute-stage MI (>48 hours from symptom onset) or early post-infarction angina;
2. MI occurring during revascularization procedures;
3. PCI-related complications (coronary artery dissection, perforation, or acute intraprocedural thrombosis);
4. Death during PCI unrelated to CMVO development;

5. Concurrent terminal illness (unrelated to primary diagnosis) with life expectancy <1 month.

The inclusion/exclusion criteria checklist is completed by the principal investigator who signs the voluntary informed consent. The completed checklist is then attached to the patient-signed informed consent document.

Diagnostic Criteria for STEMI:

1. Symptoms of acute coronary syndrome (ACS) within 48 hours prior to hospitalization (angina or equivalent symptoms);
2. ST-segment elevation (>0.1 mV in ≥ 2 contiguous ECG leads) or newly developed left bundle branch block or ST-segment depression (≥ 0.1 mV in precordial leads V1-V4) with findings suggestive of true posterior infarction;
3. Cardiac troponin levels exceeding the 99th percentile of the upper reference limit.

Definition of CMVO and Description of Used Angiographic Scales

According to the 2017 European Society of Cardiology clinical guidelines for the management of STEMI patients [12], CMVO is defined as inadequate myocardial perfusion after successful mechanical restoration of the infarct-related artery (IRA) lumen.

Criteria of Inadequate Myocardial Perfusion (at least one required for CMVO registration):

1. IRA blood flow <3 points by TIMI flow grade [8];
2. Myocardial perfusion <2 points by Myocardial Blush Grade (MBG) [13].

Other causes of coronary artery obstruction (spasm, dissection, thromboembolism) must be confidently excluded.

Procedure for Signing the Voluntary Informed Consent

The voluntary informed consent is signed by the patient in the catheterization laboratory immediately after completion of PCI. The inclusion/exclusion criteria

checklist and the signed voluntary informed consent form constitute part of the primary study documentation. These documents are placed in the patient file, which is stored at the research center.

Protocol for Blood Sample Collection, Storage and Transportation

The study utilizes human whole peripheral blood. Blood samples are collected in the catheterization room immediately after the patient signs the voluntary informed consent form. The test tube is labeled with the patient's serial number, initials, and blood collection date/time. Sample collection, preprocessing and storage are performed according to the manufacturer's protocol for the DNA extraction kit from biological material. The following reagent kits are used in this study: "CardioGenetics Hypertension", "CardioGenetics Thrombophilia", "Folate Metabolism Genetics" (manufactured by DNA-Technology, Russia), "SNP-Express-Cardiogenetics" RV kit for detecting Lys198Asn SNP in the EDN1 gene (manufactured by Litech, Russia).

Whole peripheral blood is collected in 2.0 ml or 4.0 ml Vacuette vacuum plastic tubes containing EDTA anticoagulant at a final concentration of 2.0 mg/ml (lavender-top tubes). Sodium citrate may also be used as an alternative anticoagulant. After collection, the tube should be inverted 2-3 times to mix blood with the anticoagulant. Heparin must not be used as an anticoagulant.

Prior to transportation, samples must be stored in a medical refrigerator at 2-8°C. Collected samples must be delivered to the genetics laboratory within 24 hours of blood collection. Transportation must be performed using a specialized thermal container maintaining 2-8°C.

Completion of Patient Registry Card with Hospitalization Course and Outcomes

At the conclusion of the current hospitalization, the principal investigator completes a registry card for each patient containing information about the course and outcomes of the hospitalization. The card is anonymous, recording only the patient's serial number and initials within the study. This card forms part of the

primary documentation and is stored in the patient's file at the research center. The registry card includes: details of the performed PCI; documented risk factors for CMVO development; laboratory test results (complete blood count, biochemical blood analysis, brain natriuretic peptide, etc.); instrumental diagnostic findings (ECG, ECG monitoring, echocardiography, 6-minute walk test); complications occurring during hospitalization (ventricular fibrillation, etc.); hospitalization outcome (discharged/deceased). This information is collected solely for registry purposes to enable subsequent statistical analysis. All described laboratory and instrumental diagnostic methods are performed according to standard clinical protocols for MI patient management and their use is unrelated to the study procedures. Copies of all test results are stored anonymously in the patient file. Patient angiograms are also preserved in anonymized form at the research center.

Purpose and Methodology of Genetic Analysis

The purpose of genetic analysis is to identify SNPs serving as predictors of CMVO development during PCI in patients with MI. For the study, SNPs were selected from the "CardioGenetics Hypertension", "CardioGenetics Thrombophilia" and "Folate Metabolism Genetics" panels manufactured by "DNA-Technology" (Russia), as well as the kit for determining the Lys198Asn SNP in the EDN1 gene manufactured by "Litech" (Russia) (Appendix A). This selection is based on literature data indicating that the pathogenetic changes associated with these SNPs are similar to the mechanisms of CMVO development [1].

For the panels from "DNA-Technology", SNP detection will be performed using real-time polymerase chain reaction (PCR) with high-resolution melting curve analysis using TaqMan fluorescent probes. The method principle involves amplification (copying) of DNA fragments containing SNPs through repeated cycles of: 1) thermal DNA denaturation, 2) primer annealing to DNA sequences complementary to the studied fragment, 3) extension of polynucleotide chains from these primers using Taq polymerase. The planned kit includes a "hot start" feature to increase reaction sensitivity and specificity, achieved through the use of antibody-

blocked Taq polymerase (which prevents nonspecific primer annealing to DNA targets during initial tube heating).

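### Consent and blood sampling are tied to the catheterization laboratory right after PCI although genotype can be read at any time, so living patients who cannot sign then are lost, probably more often from CMVO+

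*Protocol*

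**What the plan says.** The restriction appears throughout the protocol, and I found no exception.

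- **Inclusion Criteria, item 1:** "Signed voluntary informed consent for study participation by the patient".
- **Inclusion Criteria, item 4:** "Enrollment in the study immediately after PCI with possibility of blood sampling in the catheterization laboratory after signing informed consent".
- **Study Design, stages 1 to 3:** screening, consent and blood sampling all take place in the catheterization laboratory, with screening immediately after PCI.
- **Procedure for Signing the Voluntary Informed Consent:** "The voluntary informed consent is signed by the patient in the catheterization laboratory immediately after completion of PCI".
- **Protocol for Blood Sample Collection, Storage and Transportation:** "Blood samples are collected in the catheterization room immediately after the patient signs the voluntary informed consent form".

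Neither document provides for later consent on the ward, consent by a representative, or a later blood draw. SAP section 7 plans a flowchart of inclusion, but not a count by group of eligible patients who could not sign.

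On who is likely to be affected, the Study Rationale lists Killip class among the predictors of CMVO and states that "CMVO substantially worsens prognosis and can be a direct cause of death". It also says that "in 5–10% of cases, PCI leads to coronary microvascular obstruction". Exclusion criterion 4 reads "Death during PCI unrelated to CMVO development", so CMVO-related deaths are not excluded by that item, although such patients could not sign after PCI.

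**The concern.** A patient who is in shock, ventilated, sedated or just resuscitated at the end of PCI cannot sign. Under the present rule that patient is ineligible even if able to sign hours or days later. Such patients are likely to be commoner in CMVO+, and matching on sex and age does not correct a difference in severity.

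Three things are at stake. The CMVO+ group under-represents severe CMVO. Each lost case is expensive to replace, because CMVO is uncommon. And if a genotype affects severity as well as occurrence, its carriers are removed selectively from the cases and the odds ratio is pulled towards 1, in a study planned with only 80% power.

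**Working it through.** **1. Does anything need that moment?**

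| Element | When it is fixed or due | Source |
|---|---|---|
| Genotype | Does not change during the stay (general knowledge, not a document statement) | Blood is used for SNP typing only: protocol, Purpose and Methodology of Genetic Analysis |
| CMVO status | TIMI flow and MBG after PCI; angiograms are kept | Definition of CMVO; Completion of Patient Registry Card |
| Delivery to the laboratory | Within 24 hours of collection, not of PCI | Protocol for Blood Sample Collection |
| Registry card | End of hospitalization | Completion of Patient Registry Card |

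No measurement depends on drawing blood in the catheterization laboratory.

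**2. The plan's own sample size.** Inputs from Study Design and SAP section 6: OR 4.0, two-sided alpha 5%, power 80%, prevalence 50%, 40 pairs of which 20 discordant.

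- P = 4/(1+4) = 0.8.
- Discordant pairs m = [(1.96/2 + 0.8416 × √(0.8 × 0.2))/(0.8 − 0.5)]² = 19.26, so 20.
- At 50% prevalence in controls, 80% of cases are carriers. The probability of discordance is 0.5 × 0.2 + 0.8 × 0.5 = 0.50.
- Pairs = 19.26/0.50 = 38.5, so 39 against 40 stated. The figure reproduces.

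**3. Effect of the loss on the SNP odds ratio.** Let u1 and u0 be the shares of carrier and non-carrier cases unable to sign, and let loss among controls not depend on genotype. Then observed OR = 4 × (1 − u1)/(1 − u0). The documents give no value for u1 or u0, so these are assumptions. Power is for the uncorrected McNemar test, enumerated over discordant pairs distributed as Binomial(40, 0.5).

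| u1 v u0 | Observed OR | Power |
|---|---|---|
| equal | 4.00 | 81.6% if 40 pairs are still reached |
| 20% v 10% | 4 × 0.80/0.90 = 3.56 | 75.4% |
| 30% v 10% | 4 × 0.70/0.90 = 3.11 | 67.0% |

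With 80% of cases carriers, the last two rows mean that 0.8 × 20% + 0.2 × 10% = 18% and 0.8 × 30% + 0.2 × 10% = 26% of all CMVO+ patients cannot sign.

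**4. Recruitment.** If 10%, 20% or 30% of CMVO+ patients cannot sign, 40 cases need 40/0.9, 40/0.8 or 40/0.7, that is 45, 50 or 58 CMVO+ patients. At 10% incidence, PCI patients rise from 400 to 445, 500 or 572. At 5% they rise from 800 to 889, 1000 or 1143. This holds whether or not genotype matters.

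**5. How much later consent recovers.** Suppose 30–50% of those unable to sign die before they can. The remaining loss is then 30–50% of u1 and u0.

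- 20% v 10%: 4 × 0.90/0.95 = 3.79 to 4 × 0.94/0.97 = 3.88.
- 30% v 10%: 4 × 0.85/0.95 = 3.58 to 4 × 0.91/0.97 = 3.75.

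**6. In-hospital mortality.** Assume a share f = 10–30% of CMVO+ cannot sign, m = 30–50% of these die, and 6% of the rest die. None of these figures is in the documents; the 6% is illustrative.

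- All CMVO+: f × m + (1 − f) × 6% = 8.4% to 19.2%.
- Seen under the present rule: 6%.
- Seen with later consent, if deaths among those unable to sign come before capacity returns: (1 − f) × 6% / [(1 − f) + f × (1 − m)] = 4.6% to 5.7%.

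Later consent adds survivors to the denominator while those deaths stay out.

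**The case against.** **The odds-ratio bias is conditional.** This stands. The SNPs were chosen because their effects resemble CMVO mechanisms, and the stated objective is CMVO development, not severity. No genotype–severity relation is documented. The scenarios above are also strong: 20% v 10% and 30% v 10% are odds ratios for inability to sign of (0.20/0.80)/(0.10/0.90) = 2.25 and (0.30/0.70)/(0.10/0.90) = 3.86, the second close to the design OR itself.

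**A fixed moment of entry has value.** This also stands. Both groups now enter before the hospital course is known. The principal investigator assesses eligibility, allocates groups and completes the outcome card, and controls are selected from a pool. A longer window could let knowledge of the course influence who is approached and paired, so it needs a safeguard.

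**Two stronger readings fail.** A reader might infer that the control group loses almost nobody. The documents do not support this: controls are STEMI patients too, and some will be unable to sign. Killip class and prognosis support the direction of the imbalance only. A reader might also infer that later consent would correct in-hospital mortality in CMVO+. Step 6 shows that it can move the observed figure further from the truth. The SAP lists mortality as a secondary endpoint but gives no analysis for it.

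**The SAP already has a flowchart.** True, but it does not specify a breakdown by group or reason.

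**Conclusion.** The concern holds as a matter of avoidable selection. The rule is explicit, no study measurement needs it, and it excludes living patients who could consent later. That the loss falls more heavily on CMVO+ is an inference from the protocol's own statements on Killip class and prognosis; its size cannot be derived from the documents.

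Two consequences do not depend on genotype: a milder case group, and wasted cases (45 to 58 CMVO+ patients for 40 cases at an assumed 10–30% loss). Bias in the SNP odds ratio needs the further assumption that inability to sign depends on genotype among cases. If it does, OR 4 could be seen as 3.56 or 3.11 under the losses assumed; if it does not, there is no bias. The change is worth making because it is cheap and reduces the selection, but it is not a full correction.

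**What to change.** Amend inclusion criterion 4, stages 2 and 3, the consent procedure and the blood-collection section along these lines:

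*Consent and blood sampling take place in the catheterization laboratory when the patient is able to sign, otherwise as soon as the patient is able, before discharge from the index hospitalization. This applies to both groups. CMVO status remains as assigned at PCI.*

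Add safeguards against selection on the hospital course:

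- Log every eligible patient at PCI, with CMVO status, and approach them consecutively.
- Select each matched control by a fixed rule (same sex, age within 5 years, nearest PCI date), without regard to hospital course.
- In the flowchart, report by group the eligible patients never able to sign, including those who died first.
- Do not present in-hospital mortality among enrolled patients as CMVO+ mortality. Report deaths before consent alongside it.

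The cost is a wording amendment, an eligibility log and some blood draws on the ward. The planned 40 pairs and the laboratory tests do not change. Patients who die before they can sign are still missed, so the OR is only partly restored.

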3.2 Sensitivity Analysis

- Re-run analysis using dominant/recessive genetic models

4. Outcome Measures

- Primary endpoint: CMVO
- Secondary endpoints:
 - In-hospital mortality

- Left Ventricle Ejection Fraction
- Ventricular fibrillation
- N-terminal Pro-brain Natriuretic Peptide
- Six-minute Walk Test

5. Statistical Software

- R

6. Sample Size Justification

- 80 patients (40 CMVO+/40 CMVO-) provides:
 - 80% power to detect $OR \geq 4.0$ ($\alpha=0.05$, two-tailed)
 - Assumes SNP prevalence = 12–69% (average 50%)

7. Data Presentation

- Tables:
 - Baseline characteristics (Me [Q1; Q3] for continuous; n (%) for categorical)
 - SNP frequencies by group
 - Multivariate ORs for CMVO predictors
- Figures:
 - Flowchart of patient inclusion
 - Forest plot of significant SNPs

8. Ethical Considerations

- All analyses will use anonymized data (patient serial numbers only).
- Protocol deviations documented in CONSORT flowchart.
- Approval:

Local Ethics Committee Protocol Version: 1.0

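### Ventricular fibrillation is a secondary endpoint with no time origin; its only described source covers the whole stay, including the time before PCI when CMVO cannot yet exist

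*Protocol*

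**What the plan says.** SAP 4 (Outcome Measures) lists "Ventricular fibrillation" among five secondary endpoints. It gives no window, onset rule or comparison.

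The only VF data item described is in the protocol section on completing the patient registry card. On timing, that section says: "At the conclusion of the current hospitalization, the principal investigator completes a registry card for each patient". Among the contents of the card it lists "complications occurring during hospitalization (ventricular fibrillation, etc".

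The grouping variable arises later than admission. The protocol's CMVO definition is "inadequate myocardial perfusion after successful mechanical restoration of the infarct-related artery (IRA) lumen", and Inclusion Criteria item 5 requires "Development of CMVO as a result of PCI". Item 4 sets the entry time: "Enrollment in the study immediately after PCI with possibility of blood sampling in the catheterization laboratory".

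Neither document makes the entry time the start of VF counting or asks for the time of VF onset. The exclusion for procedural events covers "PCI-related complications (coronary artery dissection, perforation, or acute intraprocedural thrombosis". Neither that item nor any other exclusion names VF or cardiac arrest before or during PCI.

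**The concern.** A hospitalization begins at admission, and PCI falls inside it. A patient with VF between admission and PCI therefore meets the card's description, whatever the later perfusion result. In a comparison of CMVO+ with CMVO-, that episode would be scored as an outcome although it came before the condition whose consequences are being examined.

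If early VF is about equally common in the two groups, it tends to hide a real difference. If it is commoner in one group, it can exaggerate a difference, reverse it or produce one from nothing. The protocol gives reason to doubt equality. Its rationale names as CMVO predictors "age, time from symptom onset to reperfusion, severity of acute heart failure (Killip classification" and others, while the pairs are matched on sex and age only. Reperfusion delay and Killip class are therefore left unbalanced by design. If early VF goes with either, it will differ between the groups.

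**Working it through.** **The plan's own figure.** No figure is stated for VF. The one design figure is the sample size, and it concerns SNPs. With OR 4.0, P = 4/(1 + 4) = 0.8. Discordant pairs needed = (1.96/2 + 0.842 × √(0.8 × 0.2))² / (0.8 − 0.5)² = 19.26, so 20. With exposure of 50% in controls and 80% in cases, the discordant probability is 0.5 × 0.2 + 0.8 × 0.5 = 0.50, which gives 20/0.50 = 40 pairs and 80 patients. The stated figure reproduces, and VF plays no part in it.

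**Order of events in the documents.** Admission → reopening of the artery during PCI → CMVO can exist → CMVO status assigned and patient enrolled at the end of PCI → discharge or death, when the card is completed. The card's window spans all of this. The card also holds PCI details and CMVO risk factors, so it is not confined to what happens after enrolment.

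**Illustration (all VF rates are assumptions).** Let *e* be the risk of VF before CMVO can exist and *l* the risk afterwards, taken as independent within each group. Then

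- risk of any VF during the stay = 1 − (1 − e)(1 − l)
- OR = [A/(1 − A)] / [B/(1 − B)], with A for CMVO+ and B for CMVO-

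Worked example: later VF 20% v 5%, early VF 5% in both. A = 1 − 0.95 × 0.80 = 0.24 and B = 1 − 0.95 × 0.95 = 0.0975. OR = (0.24/0.76)/(0.0975/0.9025) = 2.92, against (0.20/0.80)/(0.05/0.95) = 4.75 for later VF alone.

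| Later VF, CMVO+ v CMVO- | Early VF, CMVO+ v CMVO- | Whole-stay VF | OR, later VF only | OR, whole stay |
|---|---|---|---|---|
| 20% v 5% | 5% v 5% | 24.0% v 9.75% | 4.75 | 2.92 |
| 20% v 5% | 10% v 10% | 28.0% v 14.5% | 4.75 | 2.29 |
| 20% v 5% | 15% v 15% | 32.0% v 19.25% | 4.75 | 1.97 |
| 20% v 5% | 10% v 5% | 28.0% v 9.75% | 4.75 | 3.60 |
| 20% v 5% | 15% v 5% | 32.0% v 9.75% | 4.75 | 4.36 |
| 20% v 5% | 20% v 5% | 36.0% v 9.75% | 4.75 | 5.21 |
| 10% v 10% | 20% v 5% | 28.0% v 14.5% | 1.00 | 2.29 |
| 10% v 10% | 5% v 10% | 14.5% v 19.0% | 1.00 | 0.72 |

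The second row and the seventh give the same whole-stay result, 28.0% v 14.5% and OR 2.29. One comes from a true OR of 4.75 and the other from no true difference. Whole-stay data alone cannot tell them apart.

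Unequal early VF does not by itself mean inflation. With later VF of 20% v 5% and early VF of 5% in CMVO-, the whole-stay OR returns to 4.75 when A/(1 − A) = 4.75 × 0.0975/0.9025 = 0.513. Then 1 − A = 0.661, and early VF in CMVO+ is 1 − 0.661/0.80, about 17.4%. Below that the OR is diluted; above it, inflated.

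**Precision.** With 40 per group, an approximate unmatched comparison of 20% v 5% has about 53% power. It falls to 40%, 31% and 25% once early VF of 5%, 10% and 15% is added to both groups. The endpoint is underpowered either way.

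**The case against.** The strongest reply is that the SAP never says VF is compared by CMVO status. McNemar's test is specified for SNPs, conditional logistic regression is listed without a named outcome, and no table of VF by group is planned. If VF were analysed against genotype, which precedes every episode, the objection on time order would not apply. This stands, so the point is conditional on the CMVO+ v CMVO- comparison. That is the design's only grouping, but it remains an inference for this endpoint.

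Two stronger claims are tempting and are not supported:

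- A reader might infer that early VF simply dilutes the contrast. That needs roughly equal early VF in both groups. The documents give no rates, and the named CMVO predictors argue against assuming equality.
- A reader might infer that all VF up to the end of PCI precedes CMVO. The protocol has CMVO arising in the course of the intervention, once the lumen is restored, so VF in the laboratory after reopening may follow it. Counting only from the end of PCI discards such episodes. Where CMVO provoked them they belong to CMVO+ alone, so the loss could itself pull the contrast toward no difference. The fix has to allow for this.

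Three smaller points also stand. VF before admission lies outside the card's wording. Consent signed in the laboratory may keep out some patients with a recent arrest. The card itself is not reproduced, so it may already hold onset times that the summary does not mention. None of these supplies a time origin: the only window stated is the whole stay, and the SAP does not narrow it.

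**Conclusion.** The point holds in limited form. As written, VF between admission and PCI falls within the described source for a SAP 4 endpoint. In a comparison of CMVO+ with CMVO-, such VF cannot be a consequence of CMVO. Its effect may be dilution, inflation or a spurious association. The odds ratios of 1.97 to 5.21 against 4.75, and of 0.72 or 2.29 against 1.00, show how far the result could move under assumed rates and within-group independence. They do not estimate what will happen in this study.

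The reach is one secondary endpoint with no stated power. A reader might infer that the main result is compromised. It is not: the SNP-CMVO analysis and the sample size do not use VF.

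**What to change.** - **Registry card:** record VF onset as before PCI, during PCI (before or after reopening of the infarct-related artery, where known) or after PCI. ECG monitoring findings are already on the card, and test results and angiograms are kept at the centre. These may help to fill the field for patients already enrolled.
- **SAP 4:** state that VF is compared between CMVO+ and CMVO-, name the method for that comparison, and define the endpoint as first VF after the end of PCI, when CMVO status is assigned.
- **Reporting:** show VF before PCI as a baseline characteristic. Show VF during PCI separately, with a sensitivity analysis that adds, in both groups alike, VF that began after reopening.

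The cost is a timing field on the card and a few lines in the SAP. The price is fewer VF events and a wider interval for an endpoint that is already imprecise. The primary analysis and sample size need no change.
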